#### **Sensitivity analysis #3 (PFS as per investigator, including symptomatic deterioration as an event)**

PFS endpoint will be determined and analyzed using investigator's disease assessment, including symptomatic deterioration (clinical progression with no progression on imaging or M-protein per investigator) as an event. If symptomatic deterioration is observed in absence of documented disease progression per IMWG criteria, the date of progression will be the date of symptomatic

deterioration. If both symptomatic deterioration and documented disease progression per IMWG criteria are reported, the date of event will be the earliest of the date of documented progression and the date of symptomatic deterioration.

**Sensitivity analysis #4 (PFS considering initiation of further anti-myeloma treatment as an event)**

PFS endpoint will be analyzed based on IRC disease assessments, including initiation of further anti-myeloma treatment as an event. If further anti-myeloma treatment is initiated in absence of documented disease progression per IMWG criteria, the start date of the further anti-myeloma treatment will be used as the date of PFS event. If both initiation of further anti-myeloma treatment and documented disease progression per IMWG criteria are reported, the date of event will be the earliest of the date of documented progression and the start date of further anti-myeloma treatment.

**Sensitivity analysis #5**

Adherence to the protocol-defined schedule of disease assessments will be assessed by comparing the timing of disease assessments between the treatment groups (the day of the disease assessment relative to the date of Cycle 1 Day 1). If an imbalance is observed between the treatment groups, the PFS endpoint based on the IRC disease assessments will be re-derived using nominal assessments days instead the actual assessment day for progression dates and last valid tumor assessment dates. The visit windows for defining uniform progression and assessment dates are provided in [Appendix E](#). In this sensitivity analysis progression or death occurring more than 8 weeks after the last valid tumor assessment without progression will be censored.

**2.4.4.1.2 Subgroup analyses**

**Evaluation of Consistency:**

The consistency of the results from the primary analysis will be evaluated across pre-defined subgroups in patients with available results. The definition of each subgroup is defined in [Table 9](#). Depending upon the study results, additional subgroups may be examined, and subgroups with small sample sizes may be pooled to create a larger meaningful subgroup. For each subgroup, the treatment effect HR and its associated 95% confidence interval will be estimated. A forest plot summarizing the results for each subgroup will be provided.

For each pre-defined factor among the demographic/baseline characteristics defined in [Table 9](#), PFS will be analyzed using a Cox proportional hazards model with terms for the factor, treatment and their interaction. The test of the interaction will be performed at the 10% alpha level.

**Table 9 - PFS subgroup analyses: covariates investigated**

Prognostic factor	Description
Age (eCRF)	<65 vs [65 - 75[ vs ≥75 years
Number of previous lines of therapy (IRT)	(2 or 3) vs >3
Gender	Male vs female
Race	Caucasian vs Asian vs other
Region of the world (geographical)	Western Europe vs Eastern Europe vs North America vs Asia vs Other countries
Region of the world (regulatory)	Western countries vs Other countries
ECOG PS at baseline	0 or 1 vs 2
ISS staging at study entry	I vs II vs III
R-ISS staging at study entry	I vs II vs III
Cytogenetic abnormality (del(17p), t(4;14), t(14;16))	At least one vs. none
Cytogenetic abnormality del(17p)	Yes vs No
MM type at diagnosis	IgG vs non IgG
Baseline creatinine clearance (MDRD formula)	>60 ml/min vs ≤60 ml/min
Refractory to PI	Yes vs No
Refractory to lenalidomide	Yes vs No

**Evaluation of confounding:**

Since the results from the primary analysis could be impacted by confounding factors, any potential issues will be examined and, if confirmed, an exploratory analysis of the primary endpoint will be done accordingly. A multivariate Cox proportional hazards model will be used to identify prognostic factors among the demographic and baseline characteristics factors described in the table above using a stepwise selection procedure with a 15% significance level for removing effects. For significant prognostic factors identified in the multivariate model, the balance between treatment groups will be assessed. If major confounding is identified through screening for treatment group imbalances in a prognostic factor at baseline, an exploratory analysis of PFS will be done after adjusting for the prognostic factors in the multivariate Cox proportional hazards model. Differences between the adjusted and unadjusted models will be discussed in the clinical study report.

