# 1 OVERVIEW AND INVESTIGATIONAL PLAN

## 1.1 STUDY DESIGN AND RANDOMIZATION

This is a prospective, multicenter, multinational, randomized, open-label, parallel group and 2-arm study evaluating the clinical benefit of isatuximab in combination with pomalidomide and low-dose dexamethasone as compared to pomalidomide and low-dose dexamethasone for the treatment of patients with refractory or relapsed and refractory multiple myeloma who have received at least two lines of therapy including lenalidomide and a proteasome inhibitor (bortezomib, carfilzomib or ixazomib) alone or in combination and have demonstrated disease progression on or within 60 days of completion of the last therapy.

After confirmation of eligibility criteria, patients will be randomly assigned, using an interactive response technology (IRT), in a 1:1 ratio to one of the two arms:

- Isatuximab in combination with pomalidomide and low dose dexamethasone (IPd, experimental arm).
- Pomalidomide and low-dose dexamethasone (Pd, control arm).

The duration of the study for a patient will include a period for screening of up to 3 weeks. The cycle duration is 28 days. Patients will continue study treatment until disease progression, unacceptable toxicity, patient wish, or any other reason, whichever comes first.

Randomization will be stratified according to:

- Age (<75 years versus  $\geq 75$  years).
- Number of previous lines of therapy (2 or 3 versus >3).

Approximately 300 patients (150 patients per arm) will be randomized from approximately 140 sites. Patient enrollment will be stopped after progression free survival (PFS) analysis or when 300 patients will have been randomized, whichever is first.

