### 1.3 DETERMINATION OF SAMPLE SIZE

The sample size calculation is based on the primary efficacy endpoint (ie, PFS). The following assumptions were used:

- Pd arm has a median PFS of 4.0 months.
- IPd arm will have 40% risk reduction in hazard rate in comparison to Pd arm. The targeted hazard ratio is 0.60, which corresponds to an improvement in the true median progression free survival time from 4 months to 6.67 months.
- A log-rank test at a one-sided 2.5% significance level.

Based on the above assumptions, a total of 162 PFS events are needed to achieve a 90% power for the study.

Objective for OS also support the sample size calculation using the following assumptions:

- Pd arm has a median OS of 13.0 months.
- IPd will have 31.5% risk reduction in hazard rate in comparison to Pd arm. The targeted hazard ratio is 0.685 and this is expected to correspond to a difference of 6 months in median OS between the control arm and the experimental arm.
- A log-rank test at a one-sided 2.5% significance level.

- An interim analysis for efficacy assessment on OS is planned at the time of primary analysis on PFS which is estimated to occur when about 36% of the OS events will be observed. An O'Brien and Fleming  $\alpha$ -spending function will be used to obtain the nominal significance levels for the interim and final analyses of survival.

Based on the above assumptions, a total of 220 deaths are needed to achieve 80% power for the study.

Approximately 300 patients (150 in each arm) would be adequate to achieve the targeted number of events for both PFS and OS. After the PFS analysis, no additional patient will be randomized and OS analysis will be performed on the number of patients already randomized.

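### The only multi-factor adjusted PFS hazard ratio depends on stepwise selection and an undefined imbalance screen, so this robustness check is data-driven and selectively reported

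*SAP*

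**What the plan says.** The procedure in SAP 2.4.4.1.2 has three stages. A multivariable Cox model is fitted over the Table 9 factors "using a stepwise selection procedure with a 15% significance level for removing effects". Balance between arms is then assessed for the factors it retains. Finally: "If major confounding is identified through screening for treatment group imbalances in a prognostic factor at baseline, an exploratory analysis of PFS will be done". That last analysis adjusts for the prognostic factors found, and the report is to discuss how it differs from the unadjusted result.

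The SAP gives no imbalance test or threshold and no definition of what counts as major. For the stepwise step it states a removal level only.

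Nothing else supplies the same estimate unconditionally:
- The primary log-rank test and Cox model (SAP 2.4.4.1) are stratified by age and number of prior lines only.
- Sensitivity analyses 1 to 5 (SAP 2.4.4.1.1) change the event, censoring, assessor or date rules.
- The consistency models (SAP 2.4.4.1.2) take one Table 9 factor at a time, with an interaction term.
- Protocol 11.4.2.1 adds no covariate-adjusted PFS analysis.

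**The concern.** Two data-dependent choices stand before the adjusted estimate: which covariates enter, and whether the model is reported at all.

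The first is unstable because Table 9 holds overlapping factors: ISS and R-ISS, any high-risk abnormality and del(17p) alone, and two codings of region. The second is open because the trigger is undefined. Two statisticians could follow the text faithfully and disagree on whether an adjusted analysis is due and what goes into it.

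The trigger also asks the wrong question. In a randomised trial an imbalance screen asks whether allocation looks unusual by chance. What adjustment contributes depends on how strongly the factors predict PFS, and that is there whether or not an imbalance is noticed. At stake is the credibility of one robustness check: it would be reported in some realisations of the trial and not in others, with covariates chosen from the same data.

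**Working it through.** **Inputs from the documents.** SAP 1.3: "A log-rank test at a one-sided 2.5% significance level"; "The targeted hazard ratio is 0.60"; "a total of 162 PFS events are needed to achieve a 90% power for the study"; "Pd arm has a median PFS of 4.0 months"; 150 patients per arm. SAP 3: accrual of 15 per month, so 300/15 = 20 months. The documents give no covariate prevalence, covariate effect or imbalance criterion. Those used below are assumptions.

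**The plan's own figure.** Events = 4(z₀.₉₇₅ + z₀.₉₀)²/(ln HR)² = 4(1.960 + 1.2816)²/(ln 0.60)² = 42.03/0.2609 = 161.1, rounded up to 162. Power at 162 events is 90.2%. Critical HR = exp(−2 × 1.96/√162) = 0.735, against 0.734 stated. The design figures reproduce and are not in question.

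**Step 1: how often the trigger would fire.** Assume a two-sided 5% comparison per factor. Under randomisation each factor is flagged in about 5% of trials. With k independent factors, P(none flagged) = 0.95^k, which is 0.857 for k = 3 and 0.774 for k = 5. At a 10% level the figures are 0.729 and 0.590.

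**Step 2: which observed gaps would pass.** z = d/√(2p(1−p)/150).
- Prevalence 20%: standard error 0.0462, so gaps up to 1.96 × 4.62 = 9.1 points pass. An observed 8 points gives z = 1.73, p = 0.08; 10 points gives z = 2.17, p = 0.03.
- Prevalence 40%: standard error 0.0566, so gaps up to 11.1 points pass. An observed 10 points gives z = 1.77, p = 0.08.

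**Step 3: what such a gap does.** The shift in the log hazard ratio is roughly d × ln(factor HR). At factor HR 2, 0.08 × 0.693 = 0.055 and 0.10 × 0.693 = 0.069. The standard error of the log hazard ratio is about 2/√162 = 0.157, so the shift is 0.35 to 0.44 standard errors.

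**Step 4: does the effect of adjusting vanish when nothing is flagged?** Simulation: 300 patients 1:1, 20 months of uniform accrual, control median 4 months, cut-off at the 162nd event, one binary factor, conditional HR 0.60, 2,500 runs per row. The two stratification factors are not included. Results are for trials in which the 5% screen flagged nothing. The last column is the 95th percentile of the ratio between the two HRs, after removing the average shift.

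| Prevalence | Factor HR | Unadjusted HR | Adjusted HR | Ratio, 95th percentile |
|---|---|---|---|---|
| 20% | 1.5 | 0.604 | 0.599 | 1.06 |
| 20% | 2.0 | 0.609 | 0.597 | 1.09 |
| 20% | 3.0 | 0.624 | 0.596 | 1.13 |
| 40% | 1.5 | 0.604 | 0.597 | 1.07 |
| 40% | 2.0 | 0.615 | 0.595 | 1.11 |
| 40% | 3.0 | 0.639 | 0.597 | 1.17 |

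The gap between columns grows with prognostic strength and is present without any flagged imbalance. The average gap reflects non-collapsibility of the hazard ratio and is not confounding; the last column shows how far the two estimates can still differ in a single unflagged trial. With no treatment effect, both models rejected in 2.1% to 2.8% of all runs, one-sided.

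**The case against.** The case on the other side is substantial.

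- The analysis is labelled exploratory and feeds no decision rule. This stands, and it limits the point to a minor one.
- Much is already unconditional: the stepwise model itself, one-factor models and a forest plot for Table 9, and baseline characteristics by arm (SAP 2.4.1). This stands, but none of these is a treatment effect adjusted jointly for a prespecified set of factors.
- SAP Table 1 records that the evaluation of confounding was updated in version 2 after an FDA comment, which the documents do not reproduce. Removing the procedure outright could undo something that was asked for. This stands and shapes the fix.
- SAP version 3 (20-Oct-2020) follows an amendment issued after the primary analysis, and Table 10 reports PFS only at that analysis. A covariate list added now is therefore not prespecified. This stands.

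Four stronger readings are tempting but unsupported:

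- A reader might infer that the SAP treats an undetected imbalance as proof of no confounding. It states no such conclusion; it only makes the analysis conditional.
- A reader might take the power of a two-sample test as the rate at which harmful imbalances are missed; for an 8-point difference around 20%, detection is 41%. That is power against a population difference, which randomisation excludes. An observed gap either crosses a given threshold or does not (step 2), and the SAP names no test.
- A reader might infer that the primary PFS result is biased or its error rate inflated. The simulation shows neither model exceeding its level beyond sampling noise.
- A reader might credit the change with raising the trial's power. The log-rank test stays primary, so the power of a supportive model alters no confirmatory decision.

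**Conclusion.** The point holds as a minor one. SAP 2.4.4.1.2 lets the trial data choose the covariates and decide whether the adjusted PFS hazard ratio is reported, through a trigger it does not define, and no other analysis supplies that estimate. The consequence is a selective robustness check; the confirmatory result is untouched.

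The sizes are illustrative. The 86% to 77% rests on an assumed 5% screen and three to five independent factors. The simulated hazard ratios rest on one assumed binary factor with prevalence 20% to 40% and HR 1.5 to 3.0. A clinical judgement of balance, which the SAP's wording also permits, would trigger at some other rate that cannot be calculated. That the adjusted analysis is conditional, and its condition undefined, does not depend on these assumptions.

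**What to change.** In SAP 2.4.4.1.2, replace the stepwise selection and imbalance trigger with one supportive analysis that is always reported: a Cox model for IRC-assessed PFS, stratified by the IRT factors and adjusted for a short fixed list from Table 9. An example is ISS stage, high-risk cytogenetics with an unknown level (a category SAP 2.1.1 already has), ECOG PS and baseline creatinine clearance.

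State that its hazard ratio is conditional on those covariates and not comparable like for like with the primary one. Keep the stratified log-rank test as the primary test. If the FDA comment requires the existing procedure, keep it as an additional analysis and define its imbalance criterion. Disclose a list added in version 3 as chosen after the primary PFS analysis.

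The cost is SAP wording and one model on data already collected. The downside is one more supportive hazard ratio to explain in the report.

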**2.4.4.2 Analyses of secondary efficacy endpoints**

**ORR, BOR, VGPR rate and CBR**

Best overall response, ORR, VGPR rate and clinical benefit rate according to IRC and investigator assessments will be summarized on the ITT population with descriptive statistics at the time of the primary analysis on PFS (based on data collected up to the PFS analysis cut-off date). Confidence intervals will be computed using the Clopper-Pearson method.

ORR (according to IRC assessment) will be compared between treatment groups using a Cochran-Mantel-Haenszel test stratified by stratification factors as entered in the IRT.

The proportion of patients with BOR≥VGPR (according to IRC assessment) will also be compared between the 2 arms using the test as for ORR (for descriptive purpose only).

## **OS**

The analysis of OS will consist of comparison between IPd group versus Pd group through a 1-sided log-rank test procedure stratified by stratification factors as entered in the IRT (ie, age and number of previous lines of therapy).

This analysis will be performed at the time of the primary analysis on PFS (at about 36% information fraction), at the second interim analysis on OS and at the end of the study (final analysis on OS). An O'Brien and Fleming  $\alpha$  spending function will be used to obtain the nominal significance levels for the interim and final analyses of survival. The nominal significance (one-sided) level for the final survival comparisons would be of 0.0200 for 220 death events (corresponding to a HR of 0.758).

In addition, the following estimates will be provided for OS:

- The hazard ratio (HR) and its 95% CI will be estimated using the Cox proportional hazards model stratified by the same stratifications factors as those used for the log-rank test. Underlying assumptions of the Cox proportional hazard model will be assessed by graphical methods (ie, log-log graphical methods).
- OS data will be analyzed using the Kaplan-Meier method by treatment group in the ITT population:
  - Kaplan-Meier estimates of the 25th, 50th and 75th percentiles and their associated 95% CIs will be provided,
  - Number of patients at risk as well as the probabilities of surviving at least 6, 12, 18, 24 and 36 months with 95% CI will be estimated for each treatment group using the Kaplan-Meier method.
- The number of censored patients, the reasons for their censoring (ie, alive at the cut-off date, alive at the last contact before the cut-off date, and lost to follow-up) and the time between the date of last contact and the cut-off date will be summarized by treatment group.
- Kaplan-Meier curves will be plotted.

Sensitivity analyses adjusting OS for switch to subsequent anti-cancer treatment could also be performed at interim and/or final analyses (e.g. using inverse probability of censoring weighting (IPCW) method) (7).

## **PFS in the high risk cytogenetic population**

PFS will be analyzed using Kaplan-Meier methods with the same censoring rules as the primary analysis of PFS.

## **TTP, DOR, TTIR and TTBR**

These time-to-event endpoints will be analyzed using Kaplan-Meier methods.

Similarly to the primary analysis of PFS, if progression and death (excluding for TTP: only progression) are not observed before the analysis data cut-off date, TTP and DOR will be censored at the date of the last valid disease assessment not showing disease progression performed prior to initiation of further anti-myeloma treatment (if any) or the data cut-off date, whichever comes first.

If no response (PR or better) is observed before the analysis cut-off date, TT1R and TTBR will be censored at the date of the last valid disease assessment before disease progression or death, the date of the last valid disease assessment before initiation of a further anti-myeloma treatment (if any) or the analysis cut-off date, whichever comes first.

Analysis of the pre-specified secondary endpoints will be descriptive only. Any testing procedure carried out on these endpoints will be considered as exploratory.

#### **Minimal residual disease (MRD)**

The MRD status (negative, positive) will be summarized by treatment group in the ITT population using descriptive statistics. The timing (study day from first dose) of MRD negative status will also be described.

#### **Subgroup analyses**

Subgroup analyses on main prognostic factors as defined for PFS may be performed for the key secondary endpoints based on the findings, as exploratory analyses.

#### **2.4.4.3 Analyses of exploratory efficacy endpoints**

##### **PFS2 and PFS on first line of further therapy**

PFS2 and PFS on first line of further therapy will be analyzed at the time of second interim and final OS analyses. PFS2 will be analyzed using Kaplan-Meier methods, the hazard ratio and its 95% CI will be estimated using the Cox proportional hazards model stratified by stratification factors as entered in the IRT (ie, age and number of previous lines of therapy). P-value will be provided for descriptive purpose only. PFS on first line of further therapy will be summarized among patients who received at least one line of further therapy using Kaplan-Meier methods. It will be summarized separately for further therapy with daratumumab and non-daratumumab treatment.

##### ***ORR, VGPR rate and CR rate on subsequent therapy***

ORR, VGPR rate and CR rate on subsequent therapy, based on investigator assessments, will be summarized by number of subsequent line and selected drug class and agent, with descriptive statistics at the time of the second interim and final OS analyses. Confidence intervals will be computed using the Clopper-Pearson method.

#### **2.4.4.4 Multiplicity issues**

Hypothesis testing of the key secondary efficacy endpoints will be carried out. A closed test procedure will be used to control the type I error rate meaning that not further testing will be performed unless the significance level had been reached on PFS. The hierarchical procedure will be then carried out at the one-sided 2.5% significance level in the following order:

- ORR at the time of the primary analysis on PFS (first cut-off date).
- OS tested both at the time of the primary analysis on PFS (at about 36% information), and at the end of the study (final analysis on OS).

No update of PFS or ORR as per IRC will be provided at the time of final OS analysis.

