
STATISTICAL CONSIDERATIONS
	
Sample size determination:
 
Progression Free Survival: Assuming proportional hazards, a total of 162 PFS events will be needed to detect a hazard ratio of 0.6 using a log rank test at the one sided 0.025 level with a 90% power. Based on an anticipated median PFS time of 4 months in the Pd arm; this is expected to correspond to a median PFS of 6.67 months in the IPd arm.
 
Overall Survival: Assuming proportional hazards, a total of 220 death events will be needed to detect a hazard ratio of 0.685 using a log rank test at the one sided 0.025 level with 79.3% power. Calculation takes into account an interim analysis on OS at the time of PFS analysis and one additional interim analysis of OS when approximately 90% of 220 events have occurred. Based on an anticipated median OS time of 13 months in the Pd arm; this is expected to correspond to a difference of 6 months in median OS between the Pd arm and the IPd arm.
 
A maximum of 300 patients (150 in each arm) would be adequate to achieve the targeted number of events for both PFS and OS. Assuming a uniform accrual rate of 15 patients per month, cut-off dates for primary analyses of PFS and final OS will be approximately 18 and 51 months after first patient in (FPI) respectively.

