### 3 INTERIM ANALYSIS

No interim analysis is planned for PFS. However, at the time of final PFS analysis, once 162 PFS events have been observed, secondary efficacy data (ORR and OS) will be reviewed (according to the outcome of the final analysis of the primary endpoint). An interim analysis on OS will be performed at that stage. An additional interim analysis on OS will be performed when approximately 90% of events have occurred.

At the time of final PFS analysis, formal comparisons of PFS, ORR and OS will be made according to a closed test procedure at the level of 2.5% one-sided:

If an improvement in median PFS is demonstrated, the analysis on ORR and interim analysis on OS will be performed. The ORR will be tested, at the one sided 2.5%-level. Then, if the improvement in ORR is also significant, OS will be tested as a formal comparison that would allow for early stopping for overwhelming efficacy. The stopping boundaries will be derived based on the O'Brien and Fleming  $\alpha$  spending functions.

The stopping boundaries for efficacy on OS endpoint will be derived based on the O'Brien and Fleming  $\alpha$  spending functions and will depend on the actual number of deaths observed at the time of the interim analyses.

At the first interim analysis on OS, in case where exactly 80 deaths are observed, the sponsor could stop the study for overwhelming efficacy if the p-value is  $\leq 0.000184$  (corresponding to a HR of 0.448). Under current accrual assumptions of 15 patients per month and assuming an exponential distribution of PFS in both treatment groups, the 162 PFS events milestone (and interim analysis on OS) is estimated to occur at about 18 months after FPI.

At the second interim analysis on OS, the 1-sided nominal significance level to stop the study for overwhelming efficacy at approximately 90% information fraction (198 OS events) is 0.0181 (corresponding to an HR of 0.742). This is estimated to occur at about 43 months after FPI.

The final analysis of survival, provided that the survival portion of the study is not stopped early, will take place after approximately 220 deaths have been observed, which is projected to occur approximately 51 months after the first patient is randomized. The nominal significance level for the final survival comparisons will be determined by an O'Brien and Fleming alpha spending function. It would be of 0.0200 for 220 events (corresponding to a HR of 0.758).

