No update of PFS or ORR as per IRC will be provided at the time of second interim and final OS analyses. Analyses that will be provided at time of primary analysis of PFS and second interim and final OS analyses are detailed in [Table 10](#) below.

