## **4 DATABASE LOCK**

Estimated cut-off date for primary analysis of PFS will be approximately 18 months after FPI.

The estimated cut-off date for second interim analysis on OS will be approximately 43 months after FPI and for the final analysis on OS it will be approximately 51 months after FPI.

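### SAP 2.4.4.4 and 1.3 still describe one OS interim (80% power), while the rest of the SAP and the protocol plan two interims and a final test (79.3% power in the protocol)

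*SAP*

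**What the plan says.** Two SAP sections describe a single OS interim.

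- SAP 2.4.4.4, which sets the hierarchical testing order, has "OS tested both at the time of the primary analysis on PFS (at about 36% information), and at the end of the study". The word *both* closes the list at two tests.
- SAP 1.3 has "An interim analysis for efficacy assessment on OS is planned at the time of primary analysis on PFS", mentions no other interim, and ends with "Based on the above assumptions, a total of 220 deaths are needed to achieve 80% power for the study".

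The other current text has three looks.

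- SAP 2.4.4.2 (OS) adds analyses "at the second interim analysis on OS and at the end of the study (final analysis on OS".
- SAP 3 gives the stopping level for the second interim, "at approximately 90% information fraction (198 OS events) is 0.0181", and a final level of 0.0200 at 220 deaths. Its critical hazard ratios are 0.742 and 0.758.
- SAP Table 10 has a column for the second interim and final OS analyses.
- SAP 4 dates the look: "The estimated cut-off date for second interim analysis on OS will be approximately 43 months after FPI".
- Protocol 11.4.2.3, the counterpart of SAP 2.4.4.4, lists all three tests. Protocol 11.1, 11.4.2.2.1 and 11.5 agree with it.

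Protocol 11.1 states 79.3% power for the same 220 deaths. The protocol summary explains that figure: "Calculation takes into account an interim analysis on OS at the time of PFS analysis and one additional interim analysis of OS when approximately" (the sentence then places the added look at 90% of the deaths).

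Two smaller points. The closing sentence of SAP 2.4.4.4 on not updating PFS or ORR names only the final OS analysis, whereas SAP 3 says "No update of PFS or ORR as per IRC will be provided at the time of second interim and final OS analyses". The interim-analysis paragraph of the protocol summary puts the first OS look at about 42% of deaths, against about 36% in Protocol 11.1, 11.4.2.2.1 and 11.4.2.3.

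**The concern.** OS is a key secondary endpoint inside the confirmatory hierarchy, so the section that fixes the order and number of tests should be complete. As written, SAP 2.4.4.4 leaves out a test at which SAP 3 allows the trial to stop for efficacy. The SAP change table shows that this look was added after the primary PFS analysis, so an unambiguous written testing plan matters more than usual.

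Mixing the two descriptions would have a cost in either direction. Two looks at the printed levels would waste alpha. Three looks with a final level recalculated for two would exceed 0.025. SAP 1.3 also gives a power for the study that does not belong to the design the study now has.

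**Working it through.** **Inputs.** One-sided alpha 0.025, HR 0.685 and 220 deaths (SAP 1.3, Protocol 11.1); 1:1 allocation (SAP 1.1); looks at 80, 198 and 220 deaths (SAP 3). The documents say only that an O'Brien and Fleming spending function is used; I assume the Lan-DeMets form.

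**Formulas.**

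- Cumulative alpha at information fraction t: 2[1 − Φ(2.2414/√t)].
- Correlation of the statistics at looks i < j: √(tᵢ/tⱼ).
- Mean of the statistic at d deaths: −ln(HR)·√d/2. At 220 deaths this is 0.3783 × 14.832/2 = 2.806.
- Critical HR: exp(−2z/√d).

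**No interim.** Power = Φ(2.806 − 1.960) = Φ(0.846) = 80.1%, which reproduces the 80% in SAP 1.3.

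**With interims.**

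| Looks (deaths) | One-sided levels | Critical HR at the later looks | Power at HR 0.685 |
|---|---|---|---|
| 220 | 0.0250 | – | 80.1% |
| 80, 220 | 0.000202, 0.0249 | 0.768 | 80.1% |
| 80, 198, 220 | 0.000202, 0.0181, 0.0200 | 0.742, 0.758 | 79.2% |

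With HR 13/19 (medians of 13 and 19 months) the three-look power is 79.5%, so the protocol's 79.3% lies between the two versions of the target effect. The 80% in SAP 1.3 belongs to one interim or none. The levels and hazard ratios that SAP 3 prints for the second and final looks belong to three.

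**What the omitted look carries.** Cumulative alpha is 0.000202 at 80 deaths and 0.018145 at 198, so the second interim spends 0.018145 − 0.000202 = 0.0179. Under HR 0.685 the probability of first crossing is 3.2% at look 1, 68.2% at look 2 and 7.7% at look 3.

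**Printed levels under each reading.**

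- 0.000184, 0.0181 and 0.0200 over three looks: overall error 0.0250, power 79.2%.
- 0.000184 and 0.0200 over the two looks of SAP 2.4.4.4: overall error 0.0201, power 77.4%.
- Three looks with the two-look final level of 0.0249: overall error about 0.0286.

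**Timing of the first look.** SAP 3 and Protocol 11.5 base the first boundary on 80 deaths, and 80/220 = 36.4%. With exponential PFS (medians 4 and 6.67 months), exponential OS (13 and 18.98 months) and 15 patients per month for 20 months, 162 PFS events are expected at month 17.6, with 80.9 deaths, or 36.8% of 220. The 36% figure is consistent with this; 42% is not.

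**The case against.** The best reply is that the SAP resolves this itself. Its change table says that a look at about 90% of events was added and the final boundary updated. The OS analysis section, the interim section, Table 10 and the cut-off dates all carry three looks, and a final level of 0.0200 makes sense only with three. A statistician following the SAP would be very unlikely to run two. SAP 1.3 derives its 80% from the single interim it lists, and for that design the figure is right.

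Much of this stands. No power figure is miscalculated for the design it describes; the fault is inconsistency. The shares of alpha and power at the second interim describe that look, and would be losses only if it were dropped. The demonstrated error in stated power is 0.7 points. The sentence on PFS and ORR updates is incomplete, not contradictory.

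The assumed spending function also gives 0.000202 at exactly 80 deaths, where the documents print 0.000184. The printed value corresponds to 79 deaths under that function. It is slightly conservative and leaves overall error at 0.0250.

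None of this makes the text of 2.4.4.4 correct. The multiplicity rule and the interim section of one current document give different counts of confirmatory OS tests, and SAP 1.3 presents 80% as the power of the study.

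**Conclusion.** The point holds and should be corrected. SAP 2.4.4.4 and 1.3 were left at the one-interim design when version 3 added the second OS interim. The stated power is 80% where the three-look plan gives 79.3% (79.2% to 79.5% recomputed, depending on whether the target is HR 0.685 or 13/19). With the printed boundaries, type I error is controlled at 0.0250, and no conclusion about sample size or event target changes. The power and level calculations rest on proportional hazards, the usual log-rank approximation and Lan-DeMets O'Brien-Fleming spending. The conflict between the sections does not depend on them.

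**What to change.** - **SAP 2.4.4.4:** list three OS tests, at about 36%, about 90% and 100% of 220 deaths, as in Protocol 11.4.2.3. Give 0.0181 and 0.0200 as the levels for 198 and 220 deaths, and refer to SAP 3 for the rule that boundaries follow the actual number of deaths. Extend the sentence on PFS and ORR updates to the second interim as well as the final OS analysis.
- **SAP 1.3:** add the second interim at about 90% of deaths and replace 80% with 79.3%.
- **Protocol summary, interim analysis (minor):** replace 42% with 36%.

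The cost is wording only. Stated SAP power falls by 0.7 points (80 − 79.3); the 220-death target, the sample size and every boundary stay as printed. Keeping 80% power with three looks would need about 225 deaths (80.1%; 224 gives 79.9%), which the protocol does not plan and this correction does not require.
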